We plan to recruit 20 healthy subjects (18-65 years; 10 for each of the two groups) from the Portland community through IRB approved flyers posted around the OHSU campus and the city, and advertised in local media. While we do not expect that any participants will voluntarily drop from the study, unavoidable circumstances may arise and we expect to retain enough participants to collect sufficient data on intervention development, decisions on the appropriateness of our instruments, and burden to participants. In order to assure we have sufficient qualitative and quantitative data for this proposed study and any potential lost-to-follow up, we may recruit 13 people for each arm.

b) Inclusion and Exclusion Criteria

Inclusion criteria: 18-65 years of age, able to provide their consent to be in the study, available and able to participate in study activities, who can lie in supine, able to walk 15 feet, who have no prior/current regular mind-body practice inducing breath awareness or training such as yoga, meditation, Ta-Chi, Qi-Gong; a compatible device for physiological data trackers.

Exclusion criteria: inability to provide informed consent, MRI contraindications, need for muscle relaxants or anti-anxiety drugs in order to tolerate MRI, history of neurological disorders, head trauma with loss of consciousness, craniospinal disorders, spinal injury, sleep disorders, allergic or respiratory disorders, major or uncontrolled psychiatric illness or major depression, lung and heart problems, any condition requiring the use of medication that acts on the brain like stimulants, sedatives current substance abuse issues, pregnancy or nursing.

Optimization Scans:

Inclusion criteria: 18-65 years of age, able to provide their consent to be in the study, available and able to participate in 1-hour MRI scan, who can lie in supine, able to walk 15 feet.

Exclusion criteria: inability to provide informed consent, MRI contraindications, need for muscle relaxants or anti-anxiety drugs in order to tolerate MRI.

c) Vulnerable Populations

This study (K99 or R00 phase) will not include any vulnerable populations. We will not collect any information about subjects' status as prisoners, and will actively exclude pregnant women, children, neonates, and adults lacking capacity to provide informed consent.

d) Setting

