Subjects will have an initial visit of approximately 1-hour for the purposes of informed consent, review of eligibility criteria, and to receive instruction regarding the study visits.

If enrolled, each subject's first pre-intervention data collection will involve blood pressure, BMI, response to self-report questionnaires, an hour of MRI scan including CSF flow measurements.

Subjects additionally will be provided with a wearable device in order to track home practice respiration objectively over the 8-week intervention. Subjects who successfully complete pre-intervention study procedures will go through an 8-week intervention while attending weekly on-site sessions, continuing daily home practice, and using the wearable device for respiration tracking. At the end of the 8-week intervention, we will collect post-intervention outcome measures that will involve the same measures as in pre-intervention visit. Subjects will be instructed to return their wearable device during the post-intervention visit.

Subject participation. It is expected that the K99 study first participant enrollment will begin by October 2019, and that the human subject's activity, including all interventions and follow-up visits, will be completed approximately by March 2020.

Subjects may be withdrawn from research if they no longer qualify for the study or if anything is discovered that might increase the risks involved for them to complete the study procedures (e.g. high fever on the day of scan, pregnancy, or usage of contraindicated medication, inability to attend intervention sessions, etc.)

If a subject decides to terminate their participation in this research project, any partial data that may have been collected for them may still be analyzed unless they also withdraw their consent for use of their data.

Study Procedure Details.

	Visit 1 Consent	Visit 2 MRI	Visit 3-10 Intervention	Visit 11 MRI
Consent Discussion, Screening, and Study Education	X			
Review of Consent and Screening		X		X
Vitals: Temp, BP, BMI		X		X
MRI		X		X
Physiological measures during MRI		X		X
Questionnaires		X		X
Breathing Practices			X	
Physiological Data Tracking			X	
Total time	1-hour	Up to 3 hours	Up to 24 hours	Up to 3 hours

Table 1: Onsite Visit Activities

[figure not shown]

Figure 1: Flow diagram

Phone screening. Potential subjects will be contacted by the study coordinator via telephone to prescreen.

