Consent visit. The study coordinator will discuss the informed consent with the subjects as described earlier in this protocol. Subjects who agree to sign the informed consent will be asked to:

- review their inclusion/exclusion criteria including relevant medical history.
- review their current medications for inclusion/exclusion criteria.
- complete an MRI Safety Questionnaire.
- complete an emergency contacts form and an ethnicity questionnaire.
- schedule or verify a tentative date for scheduling their imaging visit.
- receive instructions on how to use the wearable device.

Enrollment and Scheduling. Subjects who are eligible for the study will be enrolled in the study, and will be scheduled for their first imaging visit. Those determined ineligible will be let known why they are not eligible for the study participation.

First imaging visit. Members of the study team will be present for the duration of the data acquisition at OHSU's AIRC.

Ongoing Consent and Safety Screening:

- The study coordinator will review the informed consent and documents collected during the first visit to make sure nothing has changed regarding the subject's eligibility.
- **Brief Baseline Physical:** The trained study member will obtain participants' vital measurements. Subjects within the acceptable vital measurements will receive instructions for the yogic breathing techniques to be performed in the MRI instrument.
- **MRI Scan:**
- After performing the instructed breathing practices, subjects will be instructed to remove all metal on themselves, and will be transferred to the 3T MR instrument.

- Subjects will be instructed to lie still in the supine position during the entire data acquisition.
- Sufficient padding will be provided to minimize head motion artifacts and prevent discomfort.
- Subjects will be provided blankets for warmth.
- MR acquisitions will include anatomical measures and non-invasive CSF flow measures.
- At the end of the MRI scan, a visit questionnaire will be administered to provide the subject with an opportunity to let the study team know how the MRI scan experience was and if there were any problems that need to be addressed.

Self-report questionnaires:

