- Both 8-week interventions will consist of 60-minute weekly group on-site sessions (1day/week) with 20-minute daily home sessions (in between on-site sessions; 6days/week) using home-aid practice materials.
- We will define a benchmark of at least 8 on-site sessions and 15-min daily^{13,14} home practice (4 days/week) in order to see the effects we propose.
- We will objectively track subjects' respiration using the wearable device that were given to subjects during the first imaging visit.
- In addition, subjects will be instructed to report the frequency and duration of their daily home practice in a logbook provided.

ii. Second imaging visit. The procedures will be as described in "first imaging visit". Subjects will return their wearable device during this visit.

iii. Study Follow up: We may ask study subjects to follow their health and breathwork practice

after the intervention, if any, through the use of phone calls or emails three times for up to 6 months. Follow up questionnaire is uploaded.

iv. **End of study participation.** After completion of the second MRI visit, subjects will be asked to complete a set of final questionnaires to let the study team know how their study experiences were and if there were any problems that need to be addressed. These final questionnaires will include a set of post-intervention questions about instructor credibility, breathwork practice feedback, qualitative end point. Documents are uploaded.

v. **Future research studies:** Subjects will be asked for participation in future research studies.

7) Data and Specimens

a) Handling of Data and Specimens

The data collected for this study will include health information in the form of current medications, personal and family medical history, and current medical and mental health status to facilitate study screening and define subject variation. Contact information will be gathered to allow scheduling, and follow up. Subjects' blood pressure, body mass index, response to self-report questionnaires, MRI data, ECG and respiration data will be compiled within the study records.

If we find out that our data needs to be saved for future research and/or sharing to other projects, we will revise the protocol to include the necessary repository elements. In that case, we may also use subjects' correlation of data with future studies through a repository.

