10) Risks and Benefits

a) Risks to Subjects

The potential risks to subjects in the proposed research are minimal. They include the following:

- Self-reported questionnaires can cause mild anxiety.
- Interventions can cause mild anxiety or discomfort. Caution will be taken by the interventionists (who are experienced certified yoga teachers) during the classes. Participants will be monitored

at frequent intervals during the study and will be followed for a sufficient period of time after the procedure to ensure stabilization of any distress/strain associated with the intervention, and for any expected and unexpected adverse events related to intervention.

- Participants may experience physical or psychological discomfort while lying supine in the MRI instrument during the MRI experiments. The non-invasive nature and the lack of ionizing radiation make the risks associated with MRI small. FDA guidelines regarding MRI usage will be strictly followed. The MRI procedure will be explained to the subjects while standard safety procedures to remove metal from the patient and screen them for MR unsafe devices will be done. Voice contact with patients will be maintained throughout the scan. The MRI makes loud beeping or thumping noises so all subjects will be offered protective earplugs to wear during scanning. To ensure subject comfort, subjects will be provided with extra paddings around head, bolsters under knees and elbows, and blankets for warmth.
- Confidentiality: Although we have made efforts to protect subject identity, there is a small risk of loss of confidentiality.

Pregnant women and children are excluded in this study.

b) Potential Benefits to Subjects

Subjects will not directly benefit from taking part in this research other than potential benefits of participating in an 8-week intervention, which may enhance quality of life, quality of sleep, and reduce existing stress.

REFERENCES

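### Feedback on the intervention itself is collected only after the second MRI visit, with no described route for subjects who leave before it

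*Combined protocol and SAP*

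**What the plan says.** Section 6, item iv fixes the timing: "After completion of the second MRI visit, subjects will be asked to complete a set of final questionnaires". The forms ask about experience of the study and any problems, and they include "post-intervention questions about instructor credibility, breathwork practice feedback, qualitative end point". The forms are held separately and cannot be seen here.

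Table 1 places questionnaires at Visits 2 and 11, the two MRI visits, and none at the intervention sessions (Visits 3 to 10).

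Section 5a expects to keep enough participants for "sufficient data on intervention development, decisions on the appropriateness of our instruments, and burden to participants". It allows for loss by permitting 13 recruits per arm where 10 are planned.

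For subjects who end participation early, section 6 (Subject participation) says that "any partial data that may have been collected for them may still be analyzed unless they also withdraw their consent" for its use. It describes no exit questionnaire and no early-termination visit. Inability to attend sessions is among its examples of grounds for withdrawal.

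**The concern.** A subject who finds the daily practice too heavy, or the sessions unsuitable, is among those most likely to leave before Visit 11. That is also the subject whose opinion is most useful for developing the intervention. Under the plan as written this person is not given the forms that ask about the intervention. Recruiting additional people restores the number of completers but does not recover the views of those who left.

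What is at stake is how far the intervention feedback can be trusted. If the two arms lose people at different rates or for different reasons, a comparison of feedback between arms would be affected as well.

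**Working it through.** The plan gives no figure on this point, so there is none to reproduce. The check is whether any described source yields intervention feedback from a subject who leaves during Visits 3 to 10.

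| Source and section | Timing | Does it cover the intervention? | Does it reach an early leaver? |
|---|---|---|---|
| Final questionnaires (6, item iv) | After the second MRI | Yes | No |
| Visit questionnaire (6, First imaging visit; procedures repeated at the second) | End of each scan | No, it concerns the scan | First scan only, before any session |
| Self-report scales and items on attitudes, expectancy and blinding (6, Self-report questionnaires) | Imaging visits | Not at Visit 2, which precedes any session | Visit 2 only |
| Logbook and wearable (6, Interventions) | During the 8 weeks | Amount of practice and respiration, not opinion | Up to the point of leaving |
| Monitoring and follow-up for distress and adverse events (10a) | During and after the intervention | Safety, not acceptability or burden | Yes, as a general commitment |
| End-of-participation discussion (5f) | When participation ends | No feedback questions are specified | Not limited to completers |
| Follow-up contact (6, item iii) | After the intervention, optional | Health and any continued practice | Not limited to completers, but only a possibility |

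Only the first row asks directly for feedback on the intervention, and it is tied to reaching the second MRI. The fifth to seventh rows show that contact with an early leaver is foreseen, but none of them carries the feedback questions.

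To see what determines the size, take any feedback item on which a higher score is more favourable:

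- C is the completers' mean, S is the mean that early leavers would have given, and m is the share of an arm that leaves without completing the forms.
- Mean for all allocated subjects = (1 − m)C + mS.
- Completers' mean minus that value = m(C − S).

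The inputs are:

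1. *m.* Section 5a expects no voluntary dropout, which gives m = 0. Its allowance of 13 recruits for 10 planned gives (13 − 10)/13 = 3/13 = 23.1% per arm, or 6/26 = 23.1% overall. One loss in 13 would be 1/13 = 7.7%.
2. *C − S.* The documents give nothing. They define no burden score, threshold or proportion, and describe one component only as a qualitative end point.

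The product therefore cannot be evaluated. Its sign can be argued: it is positive if people leave because they rate the intervention poorly, and zero if early leavers resemble completers. Over-recruitment raises the number of completers but does not alter m(C − S).

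**The case against.** The strongest reply is that burden is never named in item iv, the forms are unseen, and no section says which instrument measures burden. Section 5a mentions burden as part of a retention rationale. It is absent from the outcome measures in section 4 and from the major dependent variables in section 8. No voluntary dropout is expected. The withdrawal examples in section 6 include fever on the scan day, pregnancy and contraindicated medication, and such subjects need not think badly of the practice. Someone who stops practising may still attend Visit 11 and complete the forms. All of this stands. It limits the point to subjects who never reach Visit 11, and it rules out putting a number on the effect.

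A reader might infer that early leavers are asked nothing at all and that every piece of burden information comes from completers. The documents do not support that. Experience of the scan, and any problems with it, is asked about in the visit questionnaire at Visit 2, and the logbook and wearable record practice up to the point of stopping.

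A reader might also infer that distress which led someone to stop would go unrecorded. Section 10a commits, without condition, to frequent monitoring during the study and says participants "will be followed for a sufficient period of time after the procedure to ensure stabilization of any distress/strain associated with the intervention", and for adverse events too. Nothing ties that commitment to the optional contact in item iii.

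What the reply does not remove is the absence of any described route by which feedback on the intervention can come from a subject who leaves before Visit 11.

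**Conclusion.** The point holds in a limited form. As written, the plan obtains feedback on the intervention itself only from subjects who reach Visit 11. The intervention-development and intervention-burden information that section 5a wants would therefore come mainly from completers and is likely to look more favourable than it is. That direction rests on the assumption that at least some early leavers stop because of the intervention.

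The size cannot be estimated from the documents, and it is zero if no one leaves early. Any percentage for understated burden would need invented rates for a statistic that the plan does not define. The CSF outcomes, the listed dependent variables and the planned tests are not affected. This is an inexpensive improvement to data collection, not a fault in the main analysis.

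**What to change.** Amend section 6, item iv along these lines: *The final questionnaires will be completed after the second MRI visit or, for a subject who stops early and has not refused further contact, at the time of stopping by phone, email or REDCap. The reason for stopping will be recorded.* The documented end-of-participation discussion in section 5f is a natural occasion for this.

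Report the feedback by arm for all allocated subjects who respond, state the number not responding, and show completers separately.

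The change uses forms, contact methods and a database already in the plan. If losses stay within the section 5a allowance, it concerns at most 3 subjects per arm. The downside is one extra voluntary request to people who have stopped, some of whom will decline, so the gap may be narrowed and not fully closed.

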- We will assess each subject's response to the following self-report questionnaires during their imaging visits: quality of life (Short-Form Health Survey; SF-36¹⁷), sleep quality (Pittsburgh Sleep Quality Index; PSQI¹⁸), perceived stress (Perceived Stress Scale; PSS¹⁹), Positive Affect Negative Affect Scale - Expanded (PANAS-X)²⁰, The Patient-Reported Outcomes Measurement Information System (PROMIS)²¹, and Cognitive and Affective Mindfulness Scale-Revised (CAMS-R)²². Additionally, we will assess subject's attitudes, expectancy and blinding towards the study.

Physiological Data Tracking:

- **Respiration:** Each subject will be provided with a wearable device in order for the study team to objectively track subject respiration, thus home practice, throughout the intervention. For this purpose, we will use a commercial off the shelf monitor (Spire³). Study staff will assure that these devices remain free of potential identifiers. We will create a respiration tracker account for each user. Subjects will receive instructions on how to utilize the wearable device during the first imaging session.
- **Sleep:** A sleep tracking methodology may be implemented within the study to investigate the effects of the intervention on long-term sleep patterns – using a Fitbit tracker. Study staff will assure that these devices remain free of potential identifiers, and will create a sleep tracking account for each subject. Subjects will receive instructions on how to utilize the wearable device during the first imaging session.

Randomization. Subjects will be told they will be enrolled in one of the 8-week intervention groups for a set of breathing practices. Group allocation will be performed through a sex and age-based randomization by a study team member who will inform the subjects with which group they will be enrolled in. Neither the subject nor the investigator can choose which group the subject will be in. Subjects will be instructed and reminded not to reveal what group they are in during the study assessment visits. They will be instructed to ask the investigator if they have any questions about this kind of study.

i. 8-week interventions.

Breathing practices:

- The yogic breathwork protocol will incorporate breathing practices that will create slow deep rhythmical and large CSF flow patterns. Active control protocol will include slow breathing practices.

Interventions:

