OHSU will be the site of operations for this project. Study pre- and post-intervention outcome measures will be performed within the OHSU's Advanced Imaging Research Center (AIRC). Physical data will be stored within the AIRC's key card secured facilities within a locked cabinet when not in use. Electronic data will be stored on restricted drives on the OHSU network, within encrypted computers, and in a web-accessible REDCap database hosted on an OHSU server. AIRC has a plan for routine back-ups of all data, including encryption and physical security addressed.

Upon enrollment, subjects will be assigned a code that will be used instead of their name or other personally identifying information. Electronic files for data analysis will contain only the subject code. Codes will not contain any part of the 18 HIPAA identifiers (initials, birthdate). The key associating the codes and the subjects personally identifying information will be restricted to the PI and study staff, who must have OHSU IRB approval and therefore the OHSU required training in HIPAA compliance, in the basics of conducting research at OHSU, and in federal, state, and university requirements for conducting human subjects research.

The key will be kept secure on a restricted OHSU network drive in a limited access folder. Encrypted data transmission will be used to share data with the study team. IRB approved study staff will be responsible for gathering study data, for coordinating its analysis, and for its archiving within the data repository in the case our study needs a repository. Data then will be shared to the repository or other investigators by transfer within the secure OHSU network drives. If identifiable data is to be transported in any other way, it will be done by hand or by secure courier with signature confirmation of receipt. All data will be kept for a minimum of three years after the study has ended and stored in a secure OHSU electronic database that has fully patched operating systems and applications including current antivirus software with current virus definitions.

b) Sharing of Results with Subjects

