- Subjects will be told in advance of participation that the research data gathered for this study is not intended for diagnoses. Results from this study are experimental in nature and will not be provided to subjects. However, if we discover information that is important for subject health care and/or if there are any significant baseline health risk factors for the subjects, this information will be conveyed to the subjects.

- Subjects will be asked if they want to know the results. Subjects may need to have additional testing in a non-research laboratory. For non-emergency issues, subjects will be referred to their primary care provider. If they have no primary care provider, reference to three providers will be given. They would be responsible for all costs associated with any follow-up testing and medical care.
- The MRI scan is being done to answer research questions, not to examine the subject's brain for medical reasons. The research MRI scan may not show problems that may be picked up by a clinical MRI scan. Any incidental findings during the MRI procedure will be communicated to the subjects. If we find an abnormality that requires urgent follow-up, we will contact subjects to help answer questions and get the right follow-up care for them. Subjects may learn information about their health that is upsetting or impacting their life in other ways.
- To minimize risks related with privacy and confidentiality, all study staff will be trained with regard to the aforementioned strict procedures and policies.

c) Data and Specimen Banking

All study data and identifiers will be banked in a repository and may be used for future research.

Access to the code list will be restricted to the repository PI and study staff. These repository personnel will have full access to the banked identifiers and coded data. Access to coded data, without any PHI, may be provided to outside investigators. IRB approval is required for release of identifiable data from this repository to outside investigators.

8) Data Analysis

Data Analysis Plan

All data recordings and analyses will be performed at OHSU. The PI will be the primary monitor working alongside the other members of the research team. MRI data quality will be assured by the MRI technologist acquiring the study. The study team will record technical notes if quality issues are present that might affect data analysis outcomes.

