Post-acquisition, each data set will be examined for quality and completeness by the trained study team.

CSF flow:

- CSF flow data analysis will be performed using a semiautomated pulsatility-based segmentation procedure. The velocity waveform will be averaged over the highly correlated ROI pixels. The maximum and minimum peak values of the averaged CSF flow velocities will then be used for analysis (see details below *Statistical Analysis*).
- The respiration frequency band and the cardiac frequency band will be defined based on the two main distinct peak amplitudes of the frequency spectrum of the averaged CSF velocity waveforms measured with RT-PCMRI.
- The relative contribution of the respiration versus cardiac component of the CSF velocity waveforms will then be quantified by defining a power ratio between respiratory component and the cardiac component.

Respiration and ECG data:

- The pulse ox and respiration data collected during the RT-PCMRI acquisitions will be filtered using a 4th order Butterworth to extract only the respiration and only cardiac component.

Wearable device:

- Respiration data from wearable device collected during the 8-week intervention will be analyzed for the respiration rate and peak-to-peak respiration intervals. If collected, sleep data measured with wearable device will be analyzed to measure the influence of intervention on participants' long-term

sleep patterns objectively.

Self-report questionnaires:

- Response to self-report questionnaires will be analyzed for the statistical analysis to compare the changes in subject's quality of life, sleep, and existing stress levels.

Statistical Analysis

- The major dependent variables will be i) CSF flow metrics maximum and minimum (values of average CSF velocities; relative ratio of respiration vs. cardiac component of the CSF velocity; ratio of the maximum CSF velocity during breathing practices to the average of peak CSF velocities at baseline during natural breathing, ii) respiration rate and peak-to-peak respiration intervals and iii) self-reported questionnaire results. The effects of the interventions on these variables will be tested in a multivariate analysis of variance with repeated measures to compare pre- and post-intervention. An alpha value of 0.05 will be used for statistical significance.

9) Privacy, Confidentiality and Data Security

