Prior to working within this study, all study members must have OHSU IRB approval and therefore the OHSU required training in HIPAA compliance, in the basics of conducting research at OHSU, and in federal, state, and university requirements for conducting human subjects research. Each member of the study team who will interact with participants, collect qualitative and quantitative instruments will be trained on addressing any participant questions.

Physical data will be stored within the AIRC's key card secured facilities within a locked cabinet when not in use. Electronic data will be stored on restricted drives on the OHSU network, within encrypted computers, and in a web-accessible REDCap database hosted on an OHSU server. AIRC has a plan for routine back-ups of all data, including encryption and physical security addressed.

Any email containing private information, referrals for recruitment for instance, will be encrypted.

At screening, participants will be assigned a unique subject identification number. Wherever possible, documents and data used in the study will be identified only by use of the participants' unique identification code. A master key list containing the subject's names and other identifiers alongside their study identification numbers will be password protected so that only the study team will have access.

Any study materials with the subjects' names or other identifiers on them (informed consent forms, recruitment response slips, emergency contacts) will be stored away from the coded subject files in a locked file cabinet.

During this study interventions, subjects will be videotaped / photographed for research/educational purposes, such as for supervision of interventions by the study team, and/or marketing purposes.

- The 60-minute on-site sessions will be videotaped by a study team member for study team's educational / research purposes.
- If subjects do not want their photographs be used for any purposes such as research/marketing publications, they will be instructed to inform the study team.
- If the study team uses a subject's photographs/recordings for research publications or marketing purposes, a black bar may be placed over subject's eyes and/or subject's voice may be disguised at their request/permission.
- If the study team uses a subject's photographs/recordings for a research publication or marketing purposes, the study team may or may not be able to inspect the photographs/recordings before they are released.

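### CSF segmentation and the post-scan quality check are not masked to arm or to pre/post visit, and the existing safeguards do not reach image reading

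*Combined protocol and SAP*

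**What the plan says.** **How the outcome is produced.** Section 8 (Data Analysis, CSF flow) states: "CSF flow data analysis will be performed using a semiautomated pulsatility-based segmentation procedure". It continues: "The velocity waveform will be averaged over the highly correlated ROI pixels". The maximum and minimum peaks of that averaged waveform go into the analysis, and they head the list of major dependent variables under Statistical Analysis. No operator is named, the manual part of the procedure is not described, and no correlation threshold is given.

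**Quality review.** At acquisition, "MRI data quality will be assured by the MRI technologist acquiring the study", and the team keeps technical notes on quality problems. Later, "Post-acquisition, each data set will be examined for quality and completeness by the trained study team". No criteria are stated, and nothing is said about what happens to a data set judged poor.

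**Who may know the arm.** Under Randomization in section 6, a member of the study team allocates subjects and tells them their group. Section 9 has a team member film the on-site sessions and gives the purposes of recording, "such as for supervision of interventions by the study team".

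**Safeguards.** Section 7a says analysis files carry only a subject code. Access to the list linking codes to identities "will be restricted to the PI and study staff". Section 6 adds: "Subjects will be instructed and reminded not to reveal what group they are in during the study assessment visits". Section 6 also lists a questionnaire item on subjects' own blinding.

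**The concern.** The hypothesis in section 4 is directional: yogic breathwork should produce larger CSF modulations than the active control. The headline metrics depend on which pixels enter the average, and a semiautomated procedure implies some operator judgement about that. If the operator knows that a scan is a post-intervention scan from the yogic breathwork arm, small choices can drift toward the hypothesis without any intent. The same applies to a quality judgement made without written criteria, if it leads to a scan being set aside.

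The instruction not to disclose group shows that the sponsor wanted some masking at assessment. The plan does not carry that through to the step where the outcome value is generated. With 10 subjects per arm, a few influenced readings could move an arm mean noticeably.

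**Working it through.** The plan gives no figure for reader variability, SD or power, so there is nothing of its own to reproduce. The check has two parts.

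**1. Do the safeguards cover image reading?**

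| Safeguard | What it hides | What it leaves open |
|---|---|---|
| Subject code on analysis files (7a) | Name | Visit is not hidden. Arm is open to anyone on the team who can connect the code to a person whose group they know |
| Restricted code list (7a, 9) | Identity, from people outside the team | The principal investigator and study staff have access |
| Non-disclosure by subjects (6, Randomization) | What subjects say at assessment visits | Arm learned through allocation or class recordings |
| Questionnaire on blinding (6) | Nothing; it measures subjects' beliefs | Masking of the reader |

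No section masks the person segmenting or the person judging quality, and none separates those tasks from allocation or class supervision. For visit, no masking is stated anywhere.

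**2. What could an arm-specific reading bias do? (hypothetical)**

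Inputs from the documents: 10 per arm (section 4), possibly 13 per arm (section 5a), alpha 0.05 (section 8). Sidedness is not stated; two-sided is assumed.

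Assumed inputs, not in the documents: reading shifts peak velocity by 5% to 10% of the mean in one arm's post-intervention scans only, and the SD of change is 20% to 30% of the mean.

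- Standardised bias: b = shift / SD. Low end 5/30 = 0.167 (rounded to 0.17); high end 10/20 = 0.50.
- Two-sample t-test with n per arm: df = 2n − 2; noncentrality = b × √(n/2).
- n = 10: df = 18, critical value 2.101. For b = 0.167, noncentrality is 0.167 × 2.236 = 0.373; for b = 0.50 it is 1.118.
- The rejection probability with no true effect is the noncentral t area beyond ±2.101.

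| b (SD) | 10 per arm | 13 per arm |
|---|---|---|
| 0 | 5.0% | 5.0% |
| 0.167 | 6.4% | 6.9% |
| 0.25 | 8.3% | 9.4% |
| 0.50 | 18.5% | 23.2% |

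**Limits of the illustration.** It uses a univariate t-test, whereas section 8 plans a repeated-measures multivariate analysis of variance. It applies to maximum and minimum velocity. A purely proportional shift would cancel in the respiratory-to-cardiac power ratio, which comes from a single waveform. It would also cancel in the practice-to-baseline velocity ratio if one region served both conditions. A bias tied to visit alone would largely cancel between arms but would distort the pre-post change, which the objective in section 2 and the analysis in section 8 both examine.

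**The case against.** The strongest reply is that the plan is silent here, not faulty, and that the silence is easily overread. Several stronger readings are tempting, and the documents do not support them:

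- **Regions drawn by hand.** The procedure is described as semiautomated and pulsatility-based, with pixels chosen by correlation. No hand drawing is mentioned, and the amount of operator input is unknown.
- **Key holders or class supervisors do the segmentation.** The segmentation sentence names nobody; only the quality check is assigned to the study team. Overlap of roles is not ruled out, but it is not stated.
- **Scans are rejected on discretion.** The plan describes examination and technical notes. It states no exclusion step.
- **The code list reveals arm.** It links codes to identities and is not said to list arm. Arm would be learned through allocation or the recordings.
- **The non-disclosure instruction is worthless.** It still protects scan acquisition, vital signs and questionnaires at the assessment visits.

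All five corrections stand. So does the objection that the error rates rest on assumed inputs: at the low end the inflation is slight, and the 18.5% needs both unfavourable assumptions together. What survives is the gap itself. Nothing in the documents prevents the reader from knowing arm and visit, and the existing measures were not designed to.

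**Conclusion.** The concern holds in a limited form. Segmentation and the post-acquisition quality check feed the main CSF velocity outcomes, neither is masked to arm or visit, and the people doing them may know both. This is an open route for bias; it is not evidence that bias will occur.

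Its size cannot be determined from the documents. The range of 6.4% to 18.5% against a nominal 5% shows only what an arm-specific bias of 0.17 to 0.50 SD would do at 10 per arm under the stated assumptions. It should not be read as an estimate for this trial. The case for acting is that the route can be closed at almost no cost, so this is a cheap improvement that the sponsor should make.

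**What to change.** Add one paragraph to section 8, under CSF flow:

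1. Before segmentation, the team member who already does allocation relabels every scan with a random file name that hides subject, arm and visit, and keeps the linking list.
2. Segmentation and any quality exclusions are done on the relabelled files, in random order.
3. Regions and exclusions are locked before the labels are linked back.
4. Where existing staffing allows, the person segmenting is neither the allocator nor a viewer of the class recordings. If a small team cannot manage this, the relabelling still removes most of the risk.

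Stating the correlation threshold and the quality criteria in the same paragraph would narrow the remaining discretion.

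**Cost:** a paragraph and a short renaming script. No extra reader and no new procedure for subjects. The one drawback is that segmentation is batched after the scans are collected and cannot proceed scan by scan. The technologist's quality check at acquisition is unaffected.
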